7.2.3 Withdrawal criteria

- (1) Acute respiratory diseases during interventions;
- (2) Acid-base imbalances during interventions;
- (3) Other severe complications that should terminate the interventions immediately;
- (4) Decide to undergo hematoma aspiration or a decompressive craniectomy;

(5) Refuse subsequent treatment and follow-up.

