10.1 Imaging test

10.1.1 Non-contrast cranial CT image

Non-contrast head CT scans are performed to assess the severity of hematoma and perihematomal edema (PHE). A 256-slice CT scanner is used following standard local protocols. Next, 5-mm-thick CT images are measured for hematoma and PHE volumes using the General Electric Company workstation built-in image software. All volume measurements are performed using a semi-automated process involving tracking the perimeter of appropriately high- and low-attenuation areas and calculating the lesion area for each slice multiplied by the slice thickness to obtain the lesion volume. Independent analysis of all images is performed by two doctors blinded to the treatment assignment, and any discrepancies are resolved consensually.

Cranial CT scans are performed at admission, day 3, 7, and 14. Software from United Imaging (United Imaging Healthcare Co., Ltd., Shanghai, China) is used for the automated calculation of hematoma and absolute PHE volumes. The relative PHE is calculated by dividing the absolute PHE volume by the baseline hematoma volume to obtain a dimensionless ratio. The reduction volumes of the hematoma, absolute PHE, and relative PHE follow the defined formula: baseline volume – follow-up volume. Besides, the clearance rate of the hematoma, absolute PHE and relative PHE are calculated as a percentage using the defined formula: $100\% \times (baseline volume - follow-up)$

volume)/baseline volume.

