10.2.3 National Institute of Health Stroke Scale (NIHSS)

The NIHSS is commonly used to evaluate neurological deficits in stroke and comprises five items in 11 fields of different neurological statuses (scores range from 0–42, representing normal to severe neurological deficits). The NIHSS is scored at admission, 3-day, 7-day and 14-day after randomization during hospitalization.

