11.1.2 Secondary outcomes

- (1) mRS distribution at 90 days.
- (2) BI scores at 90 days.
- (3) NIHSS scores at 3, 7 and 14 days.
- (4) GCS scores at 3, 7 and 14 days.
- (5) Hematoma volumes, clearance rate and reduction volume at 3, 7, 14 day.
- (6) Absolute PHE volumes, clearance rate and reduction volume at 3, 7, 14 day.
- (7) Relative PHE volumes, clearance rate and reduction volume at 3, 7, 14 day.
- (8) CBF, CBV, MTT, and TTP at 7 days.

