13.2 In-hospital periods

The patients who are assigned to the NBO group receive 100% O₂ via oxygen storage face masks (flow rate 8 L/min, 1 hour, four times daily, and 2 L/min via nasal catheter during intermittent periods, for 7 days), otherwise, the patients receive 2 L/min flow of 100% O₂ via nasal catheter for 24 hours daily for 7 days. Secondary stroke prevention follows the 2015 AHA/ASA guidelines for the diagnosis and treatment of acute intracerebral hemorrhage.⁶ Blood samples are collected at 7 days. Cranial CT is performed at 3 days, 7 days and 14 days, and cranial CTP is performed at 7 days after randomization. NIHSS score and GCS score are assessed at 7 days and 14 days after randomization.

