15.2 Statistical methods

The modified intention-to-treat analysis of efficacy outcomes and safety outcomes were performed on the full analysis set, which was composed of all patients who received randomization independent of treatment and at least 1 efficacy evaluation after enrollment. The χ^2 test was used in the unadjusted analysis. A modified Poisson regression model with robust error estimation was used to analyze the primary outcome and other dichotomous endpoints, with adjustment for prespecified covariates (age, male and onset-to-needle time). Relative risk (RR) with a 95% confidence interval (CI) was calculated in both unadjusted and adjusted analyses. Generalized linear models (GLMs) were used to analyze continuous endpoints, including NIHSS scores, Barthel scale scores, and hematoma and edema volumes. The distribution of mRS was analyzed using an ordinal logistic regression model, and odds ratios (OR) with 95% CI were calculated. Post hoc subgroup analysis was performed for the primary outcome according to age, sex, and baseline NIHSS scores, with an OR of 95% CI. No interim analyses were performed.

A 2-sided P value <.05 is considered statistical significance. Because multiple comparisons potentially cause type I error, findings for secondary outcome analyses should be interpreted as exploratory. SPSS software (version 26, IBM) and R software (version 4.1.0) are used for the statistical analyses.

16. Data Management

The enrolled participants were entered in the case report form (CRF) by the evaluator within 24 hours and entered in the electronic form within 3 days. All of the entered personnel signed on the CRF. The assessors were blinded to allocation information. A data supervisor who was not involved in clinical research is set up for data verification. Two investigators who blinded to allocation information rechecked the original data, and if the data was found to be wrong, the data should be corrected in time. The data of modification and the person who modified it should be recorded to ensure that the data is correct.

17. Data and Security Monitoring Board (DSMB)

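### Section 15.2 does not say how NIHSS, GCS and CT volumes measured at days 3, 7 and 14 are modelled within patient, or how missed visits are handled

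*Combined protocol and SAP*

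**What the plan says.** Section 11.1.2 lists "NIHSS scores at 3, 7 and 14 days", GCS at the same days, and "Hematoma volumes, clearance rate and reduction volume at 3, 7, 14 day", with parallel items for absolute and relative PHE. Section 10.1.1 gives the matching imaging schedule: "Cranial CT scans are performed at admission, day 3, 7, and 14". Section 10.2.3 does so for the clinical score: "The NIHSS is scored at admission, 3-day, 7-day and 14-day after randomization during hospitalization"; section 10.2.4 has the same schedule for GCS. Section 13.2 differs and omits day 3: "NIHSS score and GCS score are assessed at 7 days and 14 days after randomization".

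For analysis, section 15.2 states: "Generalized linear models (GLMs) were used to analyze continuous endpoints, including NIHSS scores, Barthel scale scores, and hematoma and edema volumes". GCS is not named there. The prespecified covariates (age, sex, onset-to-needle time) are attached to the Poisson model; none is stated for the GLMs. The full analysis set takes every randomized patient with one or more efficacy evaluations after enrolment. Secondary findings are declared exploratory because of multiplicity. Section 7.2.3 lists withdrawal criteria tied to clinical course, and also "Refuse subsequent treatment and follow-up".

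**The concern.** A GLM in its ordinary form treats rows as independent. With three correlated values per patient it can be run in two ways, and the plan does not choose between them.

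- **Separate model per visit.** Without imputation, each is a complete-case analysis. A patient seen only at day 3 belongs to the full analysis set but contributes nothing at day 14, and what day 3 says about that patient is discarded.
- **One model over all rows.** Three values from one patient count as three patients, so standard errors are too small.

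On neither reading does the plan state that the baseline value, recorded for every one of these measures, is used. At stake are the validity of the P values (pooled), the arm comparison if dropout is selective (separate), and some precision.

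**Working it through.** The plan gives no figure for these endpoints, so there is none to reproduce. From section 15.1: 48 patients per arm. From section 15.2: two-sided 0.05. Within-patient correlation ρ (equal between visits), dropout and effect sizes are assumptions, shown as ranges.

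**1. Rows pooled without a patient term.** With three visits the true variance of the arm difference is 1+2ρ times the variance the model assumes. Type I error = 2 × [1 − Φ(1.96/√(1+2ρ))].

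| ρ | 1.96/√(1+2ρ) | Type I error |
|---|---|---|
| 0.5 | 1.386 | 16.6% |
| 0.7 | 1.265 | 20.6% |
| 0.8 | 1.216 | 22.4% |
| 0.9 | 1.171 | 24.1% |

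**2. Separate GLMs: number of tests.** The chance of at least one false P<.05 over three visits is 1 − 0.95³ = 14.3% if independent. By simulation it is 12.5%, 10.9%, 9.8% and 8.4% at ρ = 0.5, 0.7, 0.8 and 0.9.

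**3. Separate GLMs: selective dropout (illustration).** True NIHSS effect −2 points, SD 5, 48 per arm. The chance of leaving rises with the day-3 score (logistic slope 1.2 per SD).

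| Dropout NBO v control | Complete-case day 14, ρ 0.6 / 0.8 | Likelihood estimate using day 3 |
|---|---|---|
| 5% v 15% | −1.70 / −1.60 | about −2.0 |
| 15% v 5% | −2.30 / −2.36 | about −2.0 |
| 10% v 10% | about −2.0 / −2.0 | about −2.0 |

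The first row is too small by 0.30/2 = 15% or 0.40/2 = 20%. Repeat simulations agree to within 0.03 points. The direction depends on which arm loses more patients.

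**4. Precision at day 14 from using partial data.** Missing at random, half as many missing at day 7 as at day 14. The complete-case variance is 1/(1 − proportion missing), relative to full data.

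| Missing at day 14 | Complete-case variance | Mixed-model variance, ρ 0.5 to 0.9 | Gain |
|---|---|---|---|
| 0% | 1.000 | 1.000 | 0% |
| 10% | 1.111 | 1.078 to 1.019 | 3% to 9% |
| 20% | 1.250 | 1.176 to 1.042 | 6% to 20% |

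**5. Would a day 3-14 average be a better single test?** Its variance is (1+2ρ)/3 of a single visit: 0.67, 0.80 and 0.90 at ρ = 0.5, 0.7 and 0.85. The noncentrality is (mean effect/√ratio) × √(48/2). A 0.4 SD effect at one visit gives 0.4 × 4.90 = 1.96, a power of 49%.

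| Effect at days 3, 7, 14 (SD) | Mean | Power of average, ρ 0.5 / 0.7 / 0.85 | Power at day 14 alone |
|---|---|---|---|
| 0.4, 0.4, 0.4 | 0.4 | 66% / 58% / 53% | 49% |
| 0.2, 0.3, 0.4 | 0.3 | 43% / 37% / 34% | 49% |
| 0, 0.2, 0.4 | 0.2 | 22% / 19% / 18% | 49% |

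The average wins with a constant effect and loses with these growing ones. Treatment lasts 7 days, so day 3 falls less than halfway through it and a growing effect is plausible.

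**The case against.** A reader might infer that each endpoint receives three visit-wise tests, each dropping whoever missed that visit. That is the natural default, but section 15.2 does not say so; it is equally silent on pooling. The figures in steps 1 to 3 therefore belong to alternative readings and cannot be added together or attributed to this trial.

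A reader might also infer that the day-14 results are biased. The documents do not support that. Dropout of 5% v 15% is assumed, and equal dropout gives no bias. Section 9 keeps all participants in hospital for at least 14 days, which covers every NIHSS, GCS and CT visit. Only one item of section 7.2.3 mentions refusing follow-up; the others may end treatment without ending measurement. The illustration also favours the likelihood method, because dropout there depends only on an observed score. Surgery after hematoma expansion, or death, could make values missing not at random, and a mixed model would not fully repair that.

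Multiplicity is already answered by the exploratory label, so step 2 describes a disclosed risk. Section 15.1 does cite imaging and clinical evaluations as grounds for stopping early, but it does not name these endpoints, and this modelling change would not settle that question.

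What stands after all this: the method for the repeated endpoints is unspecified, and both simple ways of filling the gap are inferior to a standard model that can be fitted to data in hand.

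**Conclusion.** The point holds as an under-specification with a better method available. If rows were pooled, type I error would be about 17-24% for ρ of 0.5-0.9. If visits were analysed separately without imputation, patients in the full analysis set would be dropped, with bias only if missingness depends on earlier scores and differs by arm. The precision gained at a single visit is nil with complete data and 3-9% with 10% missing. A claim that the repeated-measures model should yield one averaged test per endpoint goes too far: section 11.1.2 defines visit-specific outcomes and no average, and step 5 shows that the average can lose power. The primary outcome is unaffected. Severity is low to moderate.

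**What to change.** In section 15.2, for each repeated continuous endpoint (NIHSS, GCS, hematoma volume, absolute PHE, relative PHE):

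- Fit one mixed model for repeated measures with arm, visit (3, 7, 14), arm-by-visit and baseline value-by-visit, unstructured within-patient covariance, and all observed visits.
- Report the three visit-specific arm differences that section 11.1.2 defines. Show any day 3-14 average as supplementary.
- Keep the GLM for endpoints with a single follow-up, and keep these results exploratory.
- State that the model was specified after enrolment ended, that it assumes missing at random, and that surgery or death may violate this. Report the number observed per visit and arm.
- Say how reduction volume and clearance rate are handled. With baseline in the model, the arm difference in reduction volume is that in volume with the sign reversed, so it needs no model of its own; clearance rate does.
- Check residuals for NIHSS and GCS, which are bounded scores.

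Reconcile section 13.2, which omits day-3 NIHSS and GCS, with sections 10.2.3, 10.2.4 and 11.1.2; the model needs to know whether day 3 was collected.

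The cost is SAP wording and a reanalysis. No new data are needed, and SPSS and R, both already named, fit the model. The drawback is that the choice is post hoc and must be labelled so.

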11.1 Efficacy outcomes

11.1.1 Primary outcome

Primary efficacy is independence at 90 days, as scored using the mRS, and dichotomized as a good (score 0-3) or a poor outcome (score 4-6), following the Cochrane analysis of thrombolysis in stroke. The proportion of patients in each arm with good outcomes is compared at 90 days.

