15.1 Sample size calculation

The sample size was estimated according to previous trials, with an expected between-group difference of 18 percentage points in favorable outcomes (90-day mRS 0-3, 81% in the NBO group, and 61% in the control group). We set the effective size to 0.25, α error probability to 0.05, power (1- β error probability) to 0.8, and the loss rate to 10%, the final result is that the total sample size is 154. However, the interim analysis showed the profound efficacy of NBO on ICH patients demonstrated by both imaging presentations and clinical evaluations. So, we terminated the trial ahead of schedule, and enrolled 96 participants (NBO group, 48 cases, and control group, 48 cases) at last.

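### Post hoc subgroups of the primary outcome are reported as odds ratios beside a primary risk ratio, with no interaction test, so they cannot be compared with the overall effect or with each other

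*Combined protocol and SAP*

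**What the plan says.** Section 11.1.1 dichotomises the 90-day mRS into good (0-3) and poor (4-6). Section 15.2 names the model: "A modified Poisson regression model with robust error estimation was used to analyze the primary outcome and other dichotomous endpoints". It then names the effect measure: "Relative risk (RR) with a 95% confidence interval (CI) was calculated in both unadjusted and adjusted analyses".

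Later in the same paragraph the measure changes for subgroups of that same binary outcome: "Post hoc subgroup analysis was performed for the primary outcome according to age, sex, and baseline NIHSS scores, with an OR of 95% CI". No reason is given. Section 15.2 also uses an OR for the mRS distribution, but there it belongs to the ordinal logistic model and does not explain an OR for the dichotomy.

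The document gives no interaction or heterogeneity test, no subgroup model, no cut-points for age or baseline NIHSS, and no rule for interpreting subgroup results. The exploratory caveat in section 15.2 is worded for secondary outcome analyses, and these are subgroups of the primary outcome.

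**The concern.** There are two separate problems.

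The first is scale. OR and RR are close only when the outcome is rare. Here a good outcome is expected in most patients, so a table or forest plot with an overall RR and subgroup ORs puts two different quantities side by side. Subgroup effects will look larger than the effect they are meant to break down. Age and baseline NIHSS are also likely to shift the chance of a good outcome, and when control risk differs between subgroups, equal RRs do not give equal ORs.

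The second is the missing comparison. A separate estimate and interval per subgroup does not say whether the effects differ. Without an interaction estimate, the reader has only the separate intervals to compare, and in small subgroups these disagree often by chance.

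At stake is how the subgroup results are read: whether the benefit seems larger than the primary analysis found, or seems confined to some patients.

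**Working it through.** **Inputs from the documents.** Section 15.1 gives the design rates, "90-day mRS 0-3, 81% in the NBO group, and 61% in the control group", and the enrolled number, 96 (48 per arm). Section 15.2 gives the effect measures and the two-sided 5% level.

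**Assumptions.** The documents give no control risk by subgroup and no subgroup sizes. I assume two equal subgroups of 24 per arm (48/2) and vary the control risk around 61%.

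**Step 1: the two measures at the design rates.**
- RR = 0.81/0.61 = 1.33
- OR = (0.81/0.19)/(0.61/0.39) = 4.263/1.564 = 2.73

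Section 15.1 also states "expected between-group difference of 18 percentage points in favorable outcomes", whereas 81% minus 61% is 20 points. That is a separate inconsistency and does not change the conclusion: 79% against 61% gives RR = 1.30 and OR = (0.79/0.21)/(0.61/0.39) = 2.41.

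**Step 2: RR held at 1.328, control risk c varied.** Treated risk t = 1.328 × c, and OR = [t/(1−t)]/[c/(1−c)].

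| Control risk (assumed) | Treated risk | RR | OR |
|---|---|---|---|
| 50% | 66.4% | 1.33 | 1.98 |
| 55% | 73.0% | 1.33 | 2.22 |
| 61% (design) | 81.0% | 1.33 | 2.73 |
| 67% | 89.0% | 1.33 | 3.97 |
| 70% | 93.0% | 1.33 | 5.65 |

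Two equal subgroups at 55% and 67% average the design's 61%. Their ORs differ by 3.97/2.22 = 1.8-fold with no difference in RR. Wider spreads give larger ratios, but partly because the treated risk nears 100%. A constant RR of 1.33 is impossible above a control risk of 1/1.328 = 75%.

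**Step 3: the converse, OR held at 2.73.** Treated odds = 2.73 × c/(1−c). The RR is then 1.61 at c = 40%, 1.46 at 50% and 1.23 at 70%. Neither scale is free of this effect.

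**Step 4: chance disagreement between subgroups.** Both subgroups have a true 81% against 61%, with 24 per arm. If q is the probability that one subgroup reaches P<.05, exactly one of the two does so with probability 2q(1−q). Exact enumeration of the binomial outcomes gives:

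| Test within subgroup | q | Exactly one significant |
|---|---|---|
| Chi-square, uncorrected | 0.339 | 45% |
| Wald, OR | 0.309 | 43% |
| Wald, RR | 0.307 | 43% |
| Fisher exact | 0.242 | 37% |

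OR and RR intervals give the same figure, so this result bears on the missing interaction test and not on the scale. In a simulation of the same setting (200,000 runs), an interaction test rejected in about 4% of trials on either scale.

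**Step 5: what an interaction term can show here.** Within a subgroup, var(log RR) = 0.19/(0.81×24) + 0.39/(0.61×24) = 0.0098 + 0.0266 = 0.0364. For the ratio of two RRs, SE = √(2×0.0364) = 0.27. Its 95% CI runs from the estimate divided by 1.70 to the estimate times 1.70, since exp(1.96×0.27) = 1.70. Only large differences could be detected.

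**The case against.** Several points on the other side carry weight.

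- **Which scale is stable is unknown.** A reader might infer that the OR creates false heterogeneity from any constant treatment effect. The documents do not support that. It holds only if the effect is constant on the RR scale, and Step 3 shows the mirror image. What stands is that the plan chose the RR for its primary effect and left that scale, without a reason, for subgroups of the same outcome.
- **The artefact would rarely be formally significant.** With constant RR and control risks of 50% and 70%, an OR interaction test rejected in only about 7% of simulated trials. The change of scale therefore mainly distorts point estimates.
- **No misuse is written.** A reader might infer that subgroups will be judged by which interval excludes 1. The document states no such rule and makes no subgroup claim. The gap is that it supplies nothing better.
- **The analysis is labelled post hoc.** That signals that it is not confirmatory and limits the consequence. It neither aligns the scale nor provides a comparison between subgroups.
- **An interaction test is weak at this size.** True (Step 5). This argues for reporting the interaction with its interval and a caution, not for leaving it out.

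**Conclusion.** The point holds as a matter of consistency and interpretation. The change from RR to OR and the absence of any interaction test are plain in section 15.2. At the plan's own rates the two measures are 1.33 and 2.73, so the subgroup figures cannot be read against the primary result.

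The further consequences depend on assumptions. The 1.8-fold spread in ORs requires a constant RR and control risks of 55% and 67%. The 37-45% chance that exactly one of two identical subgroups is significant requires an even split of 24 per arm, and the range reflects the choice of test. The documents give neither the subgroup risks nor the subgroup sizes.

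The primary estimate, its test and the sample size are untouched. The change is worth making, but it does not threaten the trial's main conclusion.

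**What to change.** In section 15.2, replace the subgroup OR with an RR and 95% CI from the same modified Poisson model with robust errors as the primary analysis. For each of age, sex and baseline NIHSS, add a treatment-by-subgroup term and report the ratio of RRs with its 95% CI and P value. Age and sex are already covariates, so the NIHSS model also needs its main effect. State the cut-points for age and NIHSS, or enter them as continuous modifiers.

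Add two sentences: any subgroup claim rests on the interaction term and not on separate subgroup P values; and, with 96 patients, a non-significant interaction does not show that the effect is consistent. Make both changes together, because an interaction test on the OR scale would leave the mismatch with the primary measure.

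The cost is a wording change and three interaction terms fitted to existing data. The downside is that subgroup effects will look smaller than they do as ORs, and the interaction intervals will be wide.
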